Sample size for Phase 2: In Phase 2, we will conduct 12 groups (6 MAP and 6 CBT-CP) with 7 - 8 Veterans in each group to examine the feasibility of a future RCT and preliminary response to MAP (year 3 = 4 groups; year 4 = 6 groups; year 5 = 2 groups). Anticipating up to a 20% attrition rate, 86 participants will be recruited for Phase 2.

Number of Visits: Visit 1: Consent, MINI, baseline measures and actigraphy; Visits 2 - 9: MAP or CBT-CP sessions 1 - 8; Visit 10: Posttreatment measures, actigraphy; Visit 11: 3-month follow-up measures (may be done by phone); Visit 12: 6-month follow-up interview using Microsoft Teams.

Interventions. An overview of the MAP intervention is described below, as well as the CBT-CP intervention. Both groups use an 8-week, 90-minute session protocol. The MAP intervention will be delivered solely by the PI. The PI is a licensed clinical psychologist with several years of experience conducting group and individual therapy for chronic pain using mindfulness-based techniques. For the CBT-CP intervention (Phase 2 only), we will use a manualized protocol developed at the VASDHS used in previous research (Wetherell et al., 2011). In the second half of Year 2 of the award, a part-time study therapist will be hired and trained to deliver the CBT-CP intervention. This therapist will be required to have graduate (at least master's level) training in psychology, and will be recruited within the expansive VASDHS and UCSD communities. The study therapist will be supervised by [name] (co-investigator), who is a certified CBT-CP VA provider and the current supervisor for trainees in the Behavioral Medicine clinic that provide group-based CBT-CP at the VASDHS. [name] will train the study therapist and ensure competency prior to the start of Phase 2. The study therapist will have weekly check-ins with [name] via in-person or telephone while facilitating CBT-CP groups to ensure minimal drift from the protocol and to answer any questions that arise.

Description of MAP

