Initially, chi-squares and Analysis of Variance will be used to assess the effectiveness of the randomization procedures by comparing participants in each treatment condition on baseline variables. Within-group change will be assessed separately in MAP and CBT-CP groups on the primary (pain interference) and secondary clinical outcomes (pain acceptance, trait mindfulness, pain catastrophizing). We will plot means and standard deviations overtime to examine them visually, and determine the percentage of participants in each group that achieve minimally clinically important change on the BPI Pain Interference scale (1-point change, etc.). Additionally, we will use linear mixed-effects (LME) models to explore preliminary estimates of treatment effects. Time will be added as fixed effects in models, and the intercept will be added as a random effect. Effect size for within-group change will be calculated according to procedures described by Cohen, and interpreted with caution and in the context of the 95% confidence interval that surrounds it. The preliminary within-group treatment effects of MAP will help determine our future directions. For example, medium-large treatment effects would provide signal for future testing

whereas small treatment effects would suggest a need for additional development. Within the CBT-CP group, treatment effects will be examined in relation to findings from other published pain trials with similar Veteran populations to ensure adequacy of CBT-CP delivery.

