We will also conduct preliminary between-group comparisons on the BPI Pain Interference measure to better understand if continuing to pursue evaluation of MAP is warranted. Given that functional improvement is the ultimate goal of this research, we chose pain interference as the key outcome for the preliminary between-group analyses and power calculations because it is a proxy for functional improvement and one of the most commonly used outcome measure in psychosocial intervention trials of chronic pain. Group comparisons will be examined via LME with group (MAP vs. CBT-CP), time (10-total time points: baseline [1 time point], weekly during sessions [8 time points], post-intervention [1 time point]), and the treatment by time interaction added as fixed effects. The intercept will be added as a random effect. Effect size for the difference between groups will be calculated according to procedures described by Cohen. Effect size will be interpreted with caution, and in the context of the 95% confidence intervals that surrounds it.

Average time spent per week in meditation practice will be calculated from the LifeData mobile application or daily weekly diaries. The relationship between meditation practice time and study measures will be explored by adding the adherence rate to LME models as a covariate.

The actigraphy outcome will be the total activity count from each active interval, averaged across each 7-day observation period, excluding periods of missing data that occur due to temporary removal of the device. We will exclude participants that wear the Actiwatch < 5 valid days, with valid days defined as periods with < 4 hours of missing data. Participants will be instructed to press the event marker button on the Actiwatch to denote the times they get into and out of bed. Rest intervals (analogous to time in bed) will be scored manually using event markers, activity, and light, following the methodology of Patel et al. (2015), which takes into account that participants sometimes forget to press the event marker. Actigraphy data will be explored visually and via LME for trends of increased activity levels from baseline to post-intervention within group (Phase 1 and 2) and between groups (Phase 2) with guidance from [name] (statistical consultant), who has previous experience analyzing actigraphy data.

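### The MAP vs CBT-CP model for BPI interference carries baseline as one of 10 outcome points with a free arm difference and never adjusts for it, which costs precision on each reading checked

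*Combined protocol and SAP*

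**What the plan says.** The relevant text is in Section 9, Data and Data Analysis, Phase 2.

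- **Between-arm model.** "Group comparisons will be examined via LME with group (MAP vs. CBT-CP), time (10-total time points: baseline [1 time point". The list continues with eight weekly points and one post-intervention point. Group and time enter along with "the treatment by time interaction added as fixed effects". The covariance part is one sentence: "The intercept will be added as a random effect".
- **Reported effect.** "Effect size for the difference between groups will be calculated according to procedures described by Cohen". The plan does not say whether this is the interaction at the last time point, a difference in slopes, or the fitted difference at post-intervention. It does not say whether time is categorical or linear.
- **Other uses of baseline.** Before the models, "chi-squares and Analysis of Variance will be used to assess the effectiveness of the randomization procedures". No adjustment follows from these tests. The only covariate named for the mixed models is meditation adherence, explored by "adding the adherence rate to LME models as a covariate".
- **Size.** "86 participants will be recruited for Phase 2", in 12 therapy groups randomised 1:1, with up to 20% attrition anticipated.
- **Purpose.** The between-arm comparison is called preliminary, is to be read cautiously with its 95% confidence interval, and is meant to inform whether further evaluation of MAP is worthwhile. A 1-point change on BPI interference is given as the minimally important change.
- **Actigraphy.** Activity is measured at baseline and post-intervention only. It is also to be explored by mixed model for trends between groups.

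**The concern.** Having baseline in the model as a time point is not the same as adjusting for it. With an unconstrained group term, the model estimates a separate baseline mean for each arm, although randomisation makes those means equal in expectation. The interaction then subtracts the whole observed baseline difference, when only the fraction rho of it is expected to persist to follow-up.

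Two things are at stake. The confidence interval is wider than it need be, in a small pilot whose between-arm result is to be read through that interval. And for a given observed imbalance, the estimate leans towards the arm that started worse. The planned chi-square and ANOVA comparisons of baseline do not remedy either.

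**Working it through.** **Inputs from the plan.** 86 participants, so 86/2 = 43 per arm. 12 groups, so 86/12 = 7.17 per group. 10 time points, random intercept (taken to be per participant), 1-point important change.

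**Inputs not in the plan, therefore assumed.** Baseline-to-post correlation rho 0.5 to 0.8; BPI interference SD 2.2 or 1.7; baseline intraclass correlation (ICC) 0 to 0.05 within therapy groups.

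**The plan's own figure.** The plan mentions power calculations but shows no alpha, power, effect size or SD, so the 86 cannot be reproduced. It agrees with the overall total (20 + 86 = 106). The point does not depend on it.

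**Step 1: categorical time, post-versus-baseline interaction.** With complete data and a constant within-person correlation, the interaction estimate is (post difference) − (baseline difference). In SD² units, with n per arm:

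- Change score: 2(1 − rho) × 2/n
- Baseline-adjusted or baseline-constrained: (1 − rho²) × 2/n
- Ratio: 2(1 − rho)/(1 − rho²) = 2/(1 + rho)

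The half-widths use 1.96 × 2.2 = 4.312 points per unit of SE.

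| rho | SE, as planned | SE, adjusted | Variance ratio | 95% half-width at SD 2.2, points |
|---|---|---|---|---|
| 0.5 | 0.216 | 0.187 | 1.33 | 0.93 vs 0.81 |
| 0.7 | 0.167 | 0.154 | 1.18 | 0.72 vs 0.66 |
| 0.8 | 0.136 | 0.129 | 1.11 | 0.59 vs 0.56 |

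At rho 0.5 the planned contrast is no more precise than ignoring baseline altogether: √(2/43) = 0.216. With 20% uniform dropout the ratios are 1.28, 1.15 and 1.10. A simulation of 20,000 trials at rho 0.5, which estimates the covariate slope from the data, gave a ratio of 1.31. All of these ignore therapy-group clustering, so the absolute SEs and half-widths are optimistic.

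**Step 2: other readings of the plan.**

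- Linear time, slope difference, complete data: the ratio of free to constrained baseline is 1.22, 1.10 and 1.06 at rho 0.5, 0.7 and 0.8.
- Categorical time, fitted difference at post-intervention: this is the raw post difference, with variance 2/n. The ratio to the adjusted contrast is 1/(1 − rho²): 1/0.75 = 1.33, 1/0.51 = 1.96 and 1/0.36 = 2.78.

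**Step 3: shift given an observed baseline difference d.** The post difference is expected to carry rho × d. The change score subtracts d, which leaves −(1 − rho) × d. For d = 0.5 points:

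- rho 0.5: 0.5 × 0.5 = 0.25 points
- rho 0.7: 0.3 × 0.5 = 0.15 points
- rho 0.8: 0.2 × 0.5 = 0.10 points

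In the simulation at rho 0.5, the estimate regressed on d with slope −0.50 for the change score and 0.00 for the adjusted analysis. Both averaged to zero bias over randomisations.

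**Step 4: how often d reaches 0.5 points.** SE of d = SD × √(2 × DE/43), where the design effect DE = 1 + (7.17 − 1) × ICC is 1 at ICC 0 and 1.31 at ICC 0.05.

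| SD | ICC | SE of d | P(\|d\| ≥ 0.5) |
|---|---|---|---|
| 2.2 | 0 | 0.47 | 29% |
| 2.2 | 0.05 | 0.54 | 36% |
| 1.7 | 0 | 0.37 | 17% |
| 1.7 | 0.05 | 0.42 | 23% |

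**Step 5: actigraphy.** With only two time points, linear and categorical time coincide. The between-arm trend is therefore a change-score contrast under either coding, with ratio 2/(1 + rho) at actigraphy's own, unstated, rho.

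**The case against.** A reader might infer that the plan definitely specifies a change-score analysis that over-corrects and is biased. The text does not support that. The change-score identity is exact only for categorical time with the post-versus-baseline interaction, and the plan fixes neither. With linear time the loss is smaller. If the fitted post-intervention difference is reported, nothing is corrected, so over-correction would be the wrong word. Even on the change-score reading the estimator is unbiased over randomisation; the shift is conditional on the imbalance seen.

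A reader might also infer that a material baseline imbalance is likely. Step 4 gives 17% to 36%, on SDs and ICCs that the plan does not supply. Clustering from shared therapy arises only after treatment starts, so the baseline ICC may be near zero. The PEG entry threshold may also narrow baseline spread.

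The size is open too. At rho 0.7 to 0.8 the half-width shrinks by only 0.06 to 0.03 points. This is a feasibility pilot with no between-arm hypothesis or success threshold, and its worked example of a go-forward signal uses the within-group MAP effect, which arm-level adjustment does not touch.

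All of that stands and limits the point. It does not remove it: each reading checked loses precision, the leaving open of time coding and contrast is itself a gap, and the plan gives this comparison a part in deciding whether MAP is pursued.

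**Conclusion.** The point holds in a limited form. Baseline BPI interference is only an outcome in the between-arm model, its arm difference is free, and no adjustment appears anywhere in the plan. The excess variance over a baseline-adjusted contrast, for rho 0.5 to 0.8, is:

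- 33% to 11% on the natural reading;
- 22% to 6% with linear time;
- 33% to 178% if a plain post-intervention difference is reported.

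A 0.5-point observed imbalance would move the change-score contrast by 0.25 to 0.10 points, a quarter to a tenth of the plan's important change. The figures rest on an assumed rho, the stated random-intercept covariance, complete data and no clustering. This is an inexpensive gain in efficiency and clarity. It is not evidence that the planned estimate is biased or the trial unsound.

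**What to change.** In the between-group paragraph of Section 9:

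1. State how time is coded and name the contrast, for example the MAP vs CBT-CP difference at post-intervention.
2. Enter baseline BPI interference as a covariate and model only the post-baseline scores as outcomes.
3. Treat the between-arm actigraphy contrast in the same way, with baseline activity as the covariate.

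Keeping baseline as an outcome with arm means constrained equal is an alternative only if baseline is measured before allocation is known. Whole groups are randomised, and the plan does not say whether Visit 1 precedes knowledge of the group's assignment; it should. Without that, the constraint could itself introduce bias.

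As a secondary change, replace the baseline significance tests with means, SDs and standardised differences by arm.

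The cost is a wording change, because baseline is already scheduled for every participant. There is one small downside: with baseline as a covariate, participants missing baseline or all post-baseline scores do not contribute.

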The PI will meet regularly with the research team during Phase 1. In these meetings, we will discuss feedback from participants and what modifications are in order. In particular, the research team will be looking for any difficulty in understanding the concepts being presented (different approach? more or less time for discussion?), the perceived appropriateness of exercises /metaphors (did participants relate personally? do they fit with military/veteran culture?), challenges in engaging in meditation practice (to what extent did participants engage in practice outside the session? any observable discomfort or lack of engagement in the class setting? Do our measures seem to be capturing actual behavior?). Based on that material, we will modify that session in the protocol and plan for the next class session (e.g., choosing to explain again material that was not well understood, to give an alternative metaphor to assist in understanding a concept, or to modify a practice). Adjustments made to the original protocol will be incorporated into the manual and reviewed by the research team for use in the next MAP group. Decisions about protocol changes will be made by consensus among the primary research team (the PI and co-investigators). We will allow 1 month between MAP cycles to review and make refinements to the protocol. This period of time will also be used to recruit for the next group.

Procedures: Phase 2, Feasibility of MAP vs CBT-CP

In Phase 2, we will conduct a pilot randomized trial consisting of 12 groups, randomly assigning 6 groups to receive MAP or CBT for chronic pain (CBT-CP; see Description of CBT-CP below for rationale of comparison group). As in Phase 1, potential participants will be recruited primarily from the Behavioral Medicine and Primary Care clinics at the VASDHS, and other clinics as needed. Groups will be randomly assigned to MAP or CBT-CP in a 1:1 ratio based on a computer-generated randomization table produced by [name] (biostatistician consultant). The refined procedures from Phase 1 will be followed for securing consent, conducting assessments and providing compensation for participation, and the same eligibility criteria will apply. However, participants in Phase 2 will not complete weekly post-session questionnaires or mid-intervention /post-intervention qualitative phone interviews.

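### Phase 2 randomises 12 therapy groups, but the between-arm mixed model has no therapy-group term, so its 95% confidence interval is too narrow if change in pain interference clusters by group.

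*Combined protocol and SAP*

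**What the plan says.** All references are to Section 9 (Design and Methods) of the combined protocol and SAP.

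- **Allocation** (Procedures: Phase 2). The plan states "we will conduct a pilot randomized trial consisting of 12 groups, randomly assigning 6 groups to receive MAP or CBT for chronic pain", and then "Groups will be randomly assigned to MAP or CBT-CP in a 1:1 ratio". The randomised unit is the therapy group.
- **Size** (Sample size for Phase 2). There are six groups per arm, each of 7 to 8 Veterans. "Anticipating up to a 20% attrition rate, 86 participants will be recruited for Phase 2".
- **Between-arm model** (Data and Data Analysis, Phase 2). The linear mixed-effects model (LME) has arm (labelled group, and defined as MAP versus CBT-CP), time at 10 points, "and the treatment by time interaction added as fixed effects. The intercept will be added as a random effect". The unit of that intercept is not named.
- **Use of the result** (same place). The section plans "preliminary between-group comparisons on the BPI Pain Interference measure to better understand if continuing to pursue evaluation of MAP is warranted". On reading the result it says: "Effect size will be interpreted with caution, and in the context of the 95% confidence intervals that surrounds it".
- **Baseline comparison** (same place). "chi-squares and Analysis of Variance will be used to assess the effectiveness of the randomization procedures by comparing participants in each treatment condition".

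**The concern.** When whole groups are randomised, the uncertainty of the arm comparison depends on how much the groups differ from one another, and there are only 12 of them. Members of one therapy group share eight 90-minute sessions, the discussion and the calendar period, so correlated change is plausible, though the documents do not show it. A model that knows only participants and time points counts each participant as separately allocated.

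The relevant clustering is clustering of change. A stable difference in level between therapy groups cancels out of the arm-by-time term and does no harm there.

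The unnamed unit of the random intercept does not rescue the plan. With 10 measures per person, participant is the natural reading. If therapy group was meant, the repeated measures within a person are left unmodelled, and a group intercept alone still would not protect the arm-by-time contrast.

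At stake is the interval around the only randomised comparison of the primary outcome, which the plan uses to help judge whether MAP deserves further study. The baseline chi-square and ANOVA checks make the same mistake about the unit of allocation, with less consequence.

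**Working it through.** **The plan's own figures.** 12 groups × 7 to 8 = 84 to 96, which contains 86 (for example ten groups of 7 and two of 8). 20 in Phase 1 + 86 = 106, the stated total. 86 × 0.8 = 68.8, so about 69 are retained. These are headcounts. Power calculations are mentioned, but no effect size, SD, power or ICC is given, so none can be reproduced.

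**Inputs.** 12 therapy groups; mean size m = 86/12 = 7.17 recruited, or 69/12 = 5.75 retained. The ICC of change is not in the documents; 0, 0.02, 0.05 and 0.10 are assumed.

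**Formulae.** Design effect DEFF = 1 + (m − 1) × ICC. Ratio of interval widths = √DEFF × t(0.975, 10) / t(0.975, N − 2). At ICC 0 the ratio is 2.228/1.989 = 1.120 for N = 86 and 2.228/1.996 = 1.116 for N = 69.

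| | ICC 0 | 0.02 | 0.05 | 0.10 |
|---|---|---|---|---|
| N = 86: DEFF | 1.000 | 1.123 | 1.308 | 1.617 |
| N = 86: √DEFF | 1.000 | 1.060 | 1.144 | 1.271 |
| N = 86: width ratio | 1.120 | 1.188 | 1.282 | 1.425 |
| N = 69: DEFF | 1.000 | 1.095 | 1.238 | 1.475 |
| N = 69: √DEFF | 1.000 | 1.046 | 1.112 | 1.214 |
| N = 69: width ratio | 1.116 | 1.168 | 1.242 | 1.356 |

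On a standardised difference with N = 86, the half-width ignoring therapy group is 1.989 × √(4/86) = 0.43. With 10 df it is 2.228 × √(4 × 1.308/86) = 0.55 at ICC 0.05, and 0.61 at ICC 0.10.

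**Coverage of the planned interval.** This was simulated with 8,000 runs per setting: 12 groups (ten of 7, two of 8) randomised 6:6, 10 time points, no true arm effect, residual SD 1, participant intercept SD 1.5 and stable therapy-group SD 0.5. The planned model was fitted by REML with a participant intercept, arm, categorical time and arm by time. The target was the baseline-to-post arm contrast. Clustering of change was entered either as group-by-time effects or as group slopes; the ranges span both.

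| Coverage of nominal 95% interval | ICC 0 | 0.02 | 0.05 | 0.10 |
|---|---|---|---|---|
| Planned LME, all 86 | 94.9–95.0% | 93.1–93.2% | 90.7–90.8% | 85.0–87.7% |
| Planned LME, 20% random dropout | 95.0–95.1% | 93.4–93.5% | 91.3–91.7% | 86.9–88.6% |

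The t interval on the 12 group means covered 94.4–95.3% in all of these settings.

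Two side checks:

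- With stable therapy-group SD raised to 1.0 and no clustering of change, the planned LME covers 94.7%, so level differences alone are harmless for this contrast.
- With no clustering of change but participants differing in slope (SD over the treatment period 0.5 or 1.0 × the residual SD), the planned LME covers 94.0% or 90.9%, and the group means 94.9% or 95.0%.

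**A second form of the check.** This tested the arm-by-linear-time slope with 12 groups of 7, complete data and 4,000 runs. The random-intercept model rejected a true null at 5.0%, 7.6%, 9.0% and 13.6% for ICC 0, 0.02, 0.05 and 0.10. A t test on group mean slopes with 10 df stayed between 4.4% and 5.6%.

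**The case against.** The mismatch itself cannot be disputed on the text. The objections concern its weight.

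- **The comparison is preliminary.** The only numbered hypothesis (Section 6) is feasibility. The between-arm analysis has no alpha and no interval threshold, and it sits beside feasibility, satisfaction and the share reaching a 1-point change. The signal tied most directly to next steps is within-arm: "The preliminary within-group treatment effects of MAP will help determine our future directions". This stands and limits the consequence. It does not excuse the interval, because caution that relies on an interval fails if the interval is too narrow.
- **The widths overstate the plan's error.** At ICC 0 the planned interval covers 95%, so the 12% due to degrees of freedom is a cost of the remedy. On √DEFF alone the widening is 6%, 14% and 27% with 86 participants, or 5%, 11% and 21% with 69. This stands, and coverage is the fairer measure.
- **The 85% figure depends on the model.** The design effect alone at ICC 0.10 implies about 88%; the lower end comes from how clustering was entered. This stands.
- **The interval is attached to a Cohen effect size, not expressly to an LME contrast.** True. If the effect size were computed from post-intervention means, stable differences between therapy groups would no longer cancel, which does not help the plan.
- **Therapist is confounded with arm.** One therapist delivers all MAP groups and another all CBT-CP groups. No therapy-group term can remove that, and the simulations assume no therapist effect.
- **The remedies have limits.** Group means use only participants with a post value, and the simulated dropout was random. With 12 groups, a therapy-group variance may often be estimated as zero. In a simplified change-score check this happened in about 44%, 31% and 16% of runs at ICC 0.02, 0.05 and 0.10, although coverage stayed at 95–96%.

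**Conclusion.** The concern holds. The stated analysis ignores the unit of randomisation under either reading of the random intercept, and nothing elsewhere in the documents makes up for it.

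The interval is too narrow only if change clusters within therapy groups. The size depends on an ICC that the documents do not give: from a 2-point loss of coverage at 0.02 to a loss of 7 to 10 points at 0.10, with all 86 participants. These figures assume a participant intercept and the baseline-to-post contrast.

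Leaving the term out does not in itself bias the point estimate. The consequence is understated uncertainty in a preliminary comparison, not a wrong decision rule.

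**What to change.** Analyse by the randomised unit and name the level of every random effect. Either of two routes will do:

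1. Make the main between-arm estimate a comparison of the 12 group-mean changes in BPI interference, with a t interval on 10 df.
2. Fit an LME with random intercept and slope for participant and random intercept and time effect for therapy group, using Kenward-Roger or Satterthwaite degrees of freedom, and report the group-mean comparison as a check. The participant slope is needed: without it the interval is too narrow whenever participants differ in their rate of change, and that variation can be mistaken for therapy-group variance. State in advance what will be done if the therapy-group variance is estimated as zero.

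In either case, state which contrast the effect size and its interval refer to. It would also help to report the therapy-group ICC with its interval, which will be imprecise but useful for planning a later trial, and to describe baseline balance without participant-level tests. The text should acknowledge that therapist and arm cannot be separated.

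The cost is analysis wording and a few lines of code, with no new data. The interval becomes wider. Route 1 drops participants without a post value; route 2 keeps their partial data.
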